The Relational Agent will be delivering the same kind of care as the PCP would ideally deliver. The Relational Agent will be providing a form of brief Motivational Interviewing and recommending a follow-up visit in one month. The Relational Agent (whose name is Laura) will commence with a brief assessment, which will be administered in order to provide personalized feedback to the Veteran. The assessment includes the Quick Drinking Screen (QDS) and the full Alcohol Use Disorders Identification Test (AUDIT) (see Measures, below). Although the Veteran will have completed the AUD-C in the initial interaction with the primary care health technician, we will use the full AUDIT to enable us to provide the Veteran feedback about other symptoms of alcohol problems. We are also using the QDS to give feedback on drinking levels and how they compare to national guidelines. The feedback derived from these measures is a standard method of delivering feedback and using drinking problems they bring to light to try and motivate the person to change.

Next Laura will take the Veteran through the decisional balance exercise (pros and cons of change). Importance, confidence, and readiness rulers and responses to those will be used. At the end, Laura will ask for a commitment to change. If a Veteran has an alcohol use disorder, as determined below, the Veteran will be offered treatment through referral to specialty substance abuse clinics. A personal feedback report will be printed out for the Veteran that includes a summary of findings and patient input. A clinic report will also be generated that will be used to write a progress note and as data for a referral (see Appendix B for all reports).

In the second visit, one month later, Laura will again ask Veterans about their drinking, and give them feedback about how their current drinking compares to what they reported earlier. If the Veteran has reduced consumption, they will be congratulated. If they have not changed drinking patterns, Laura will give the Veteran the option to revisit sections of the motivational intervention from session 1. If they haven't changed their drinking, or if they did not follow-up on a previous referral, the Veteran will again be offered a referral to specialty care. Veterans will again receive printed feedback and a clinic report will be prepared.

Procedures

Screening Interview

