Based on the results of the MINI Alcohol Scale, the research assistant will stratify each participant as having either risky drinking or an alcohol use disorder. Veterans stratified to the risky drinking group reflect a population of individuals among whom brief interventions have been most frequently demonstrated to be efficacious. In contrast, the efficacy of brief intervention among individuals with Alcohol Use Disorder has rarely been studied. Because we undertake this study as a pragmatic clinical trial, we do not want to exclude these individuals from participation; therefore we are stratifying our sample for two purposes. First, stratification will enable us to examine a priori the effectiveness of the Relational Agent on primary and secondary outcomes separately in these two strata. As described below, we hypothesize that the effect of the intervention will vary between the two strata. Second, stratification allows tailoring of the intervention to each stratum; we will configure the Relational Agent always to recommend referral for further evaluation and treatment to Veterans in the Alcohol Use Disorder group, whereas it will only recommend referral to Veterans meeting certain response criteria within the risky drinking group (no desire to change, wish to discuss drinking with a person instead). After the research assistant determines the stratum, the research assistant and Veteran proceed to randomization.

Randomization

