When session 1 is over, the research assistant will print out the patient feedback report for the participant, and make sure they are scheduled for session 2 and the 3 month research interview. The patient feedback report will contain information about the participant's drinking and their list of pros and cons (see Appendix B). The clinic report will contain information about the participant's drinking, and whether or not a referral was agreed upon. The information from the clinic report will go into a progress note in CPRS, and will be

used for referral if needed. The research assistant will check the clinic report to see if a referral is indicated, and contact [name] or [name] if a consult (referral) is indicated. [name] or [name] will speak with the participant on the phone to gather information for the consult and place the consult for the participant. If, in the unlikely event that either [name] or [name] are not available, the research assistant will contact the postdoctoral fellow working on this project, or walk the participant down to the offices of the Primary Care Mental Health staff for assistance. If there are any concerns about suicidality or homicidality from the telephone consult process, the research assistant will walk the participant over to Primary Care Mental Health staff for assistance. If they are not available the research assistant will alert the primary care team and hand off the patient to one of the PCC staff who can bring the patient to urgent care. See “Human Subjects – Protection Against Risk” for more detail.

When the participant returns for session 2, the research assistant will again set up the computer for the participant and allow them to use the program in privacy, using headphones. At the end of the session, the research assistant will print out the patient feedback report, confirm the 3 month follow-up appointment, and check the clinic report for instructions. If a referral is needed the research assistant will follow the same procedure as above. Veterans receive \$10 in for completing questionnaires after session 2.

The research assistant will also ask the Veteran to fill out the System Usability Scale and the ECA Questionnaire.

Three-Month Follow-up Interview

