We will use these instructions and, as done by Hawkins et al, we will provide reviewers with examples that satisfy each of the above components of brief alcohol counseling. Similarly, we will follow the approach of Hawkins et al in ascertaining referral for alcohol problems. Referral to alcohol treatment will be defined as a documented discussion in CPRS of referral for VA or non-VA services to address alcohol misuse or a scheduled appointment for VA services. We will train reviewers to identify and abstract information of any referral to VA or non-VA alcohol treatment services and document type of referred services (e.g., addiction specialty care, non-VA primary care services?) and date of referral appointment. Alcohol treatment services will be defined as any of the following with documentation indicating the purpose of the service was to evaluate or address alcohol misuse: VA inpatient or outpatient specialty-care addiction services, VA alcohol-related telephone counseling, or referral to non-VA facility for alcohol treatment. Reviewers will also be instructed to indicate if a discussion of a treatment referral was documented in CPRS without actual referral being made. For Veterans who received appointments to address alcohol misuse, reviewers will ascertain the date Veterans attended their referral appointment.

In addition, we will abstract and record other Mental Health diagnoses, especially Substance Use Disorders, PTSD, and TBI, to describe the sample and examine any subgroup differences.

[name], an experienced primary care physician and active user of CPRS, will train the research assistants to conduct the CPRS review and abstraction. The research assistants will be blinded to the treatment status of the Veterans. [name], who will also be blinded to the treatment status, will oversee the data abstraction and ensure its quality and accuracy. Abstracted data will be entered into the REDCAP database for eventual conversion to SPSS format for analysis.

Study Data Management

Telephone communications. We will have one telephone line where participants or clinic staff can call and leave messages. Research staff will answer this phone or return calls promptly.

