Alcohol use and related behaviors will be assessed by in-person survey at baseline and by telephone survey at 3 months after randomization. Principal intervention effect analyses will be performed at 3 months. The primary dependent (outcome) variables are number of drinking days per week (frequency) and average drinks per drinking day (quantity). Secondary dependent variables are percent receiving brief intervention and percent referred for further evaluation or treatment of alcohol problems.

Independent Variables

The two independent variables are the experimental condition, Treatment as Usual vs. Treatment as Usual plus Relational Agent Intervention, and the severity of alcohol use, dichotomized as Risky Drinking vs. Alcohol Use Disorder. The experimental condition will be assigned by random allocation (see Section 4.e.7).

The severity of alcohol use variable, which will be used to allocate Veteran-participants into two strata prior to randomization, will be ascertained by the baseline completion of the MINI.

Dependent Variables

The primary dependent variables (i.e., the main study outcome measures) are **number of drinking days per week** and **average drinks per drinking day**. Because the Relational Agent will target reduction of both the frequency (number of drinking days per week) and the quantity (average drinks per drinking day) of alcohol consumption, each of these measures will be considered separately as primary outcome measures. These variables are measured by the QDS.

Secondary dependent variables include **completion of brief intervention** (yes/no) and **referral for evaluation/treatment** (yes/no); these secondary dependent variables will be ascertained from review of CPRS. We will also ascertain completion of brief intervention and referral for evaluation/treatment from the interviews with participants; we will assess concordance between CPRS and Veterans' self-report and, for main analyses, we will count brief intervention or referral as completed if they are ascertained from either source.

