For our secondary outcome of increased rate of delivering brief intervention, we will compare the two study groups on the proportion of patients receiving brief intervention through the chi-square test. Logistic regression will be used to calculate odds ratios and 95% confidence intervals in order to describe differences in rates of brief intervention between groups. To further examine baseline patient characteristics that predict brief intervention, and control for any covariates found to differ between treatment groups at baseline, we will develop a multivariable logistic regression model predicting rate of brief intervention from baseline characteristics as well as indicator variables representing the intervention group and presence/absence of alcohol use disorders.

Secondary Hypothesis: The Relational Agent will be more effective than Treatment as Usual in improving rates of referral to specialty treatment.

Secondary analysis also includes a comparison of referral rates, and analyses similar to those described for the secondary Hypothesis above will be employed. We will compare study groups on the proportion of patients referred through the chi-square test. Since we expect that Veterans with alcohol use disorders will be more likely to be referred regardless of group, we will test this hypothesis separately, i.e., we will use chi-square to compare rates of referral based solely on presence or absence of alcohol use disorders. Logistic regression will be used to calculate odds ratios and 95% confidence intervals in order to describe differences in referral rates between groups. To further examine baseline patient characteristics that predict brief intervention, and control for any covariates found to differ between treatment groups at baseline, we will develop a multivariable logistic regression model predicting referral rates from baseline characteristics as well as indicator variables representing the intervention group and presence/absence of alcohol use disorders.

Additional exploratory hypotheses:

Negative consequences for alcohol use, as measured by the SIP, may also decrease as a result of intervention, and this hypothesis will be explored as well through a random effects linear regression model.

Sample Size and Power Considerations

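### As written, a referral offer from the agent that the Veteran declines can score as a referral, and no rule says how discussion-only cases are counted

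*Combined protocol and SAP*

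**What the plan says.** **Definition.** Under Review of the Computerized Patient Record System (CPRS), "Referral to alcohol treatment will be defined as a documented discussion in CPRS of referral for VA or non-VA services"; a scheduled VA appointment is the alternative. Discussion alone is enough.

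**Flag.** The same section adds: "Reviewers will also be instructed to indicate if a discussion of a treatment referral was documented in CPRS without actual referral being made".

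**What the agent does.** Under Stratification, "we will configure the Relational Agent always to recommend referral for further evaluation and treatment to Veterans in the Alcohol Use Disorder group". In the risky-drinking stratum it recommends referral only to "Veterans meeting certain response criteria within the risky drinking group (no desire to change, wish to discuss drinking with a person instead"). The section on the intervention procedure adds previous substance abuse treatment and a high AUDIT score as triggers. At the second session, if drinking is unchanged or an earlier referral was not followed up, "the Veteran will again be offered a referral to specialty care".

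**What reaches the chart.** The clinic report records the Veteran's drinking and "whether or not a referral was agreed upon", and its content is entered as a CPRS progress note. Potential Risks likewise says that a research progress note documents the recommended actions.

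**Usual care.** Under Study Arms, a TAU clinician may choose to refer. TAU+RA Veterans keep usual care as well.

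**Scoring and analysis.** Under Dependent Variables, "for main analyses, we will count brief intervention or referral as completed if they are ascertained from either source". Under Statistical Analysis, "We will compare study groups on the proportion of patients referred through the chi-square test", followed by logistic regression. Neither place mentions the flag.

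**The concern.** The definition makes a charted discussion sufficient, and the intervention itself writes such a discussion into the chart of many TAU+RA participants. If the Veteran declines, no consult follows, yet the entry can still meet the definition. TAU has no counterpart to this note, so assignment itself can raise the scored rate.

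The CPRS section is also in tension with itself. It treats discussion as referral and then asks abstractors to separate discussion from actual referral. With no scoring rule, two analysts could derive different endpoints from the same charts.

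At stake is the secondary hypothesis that the agent improves rates of referral to specialty treatment. It could be reported as supported when the arms differ mainly in charted offers. The primary outcomes come from the Quick Drink Screen and are not affected.

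**Working it through.** **No plan figure to reproduce.** The documents give no referral rate, target difference or power for referral. The one power table concerns the drinking outcomes.

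**Inputs from the documents**
- 180 participants in two arms: 90 per arm, or 63 per arm at 30% loss to follow-up.
- AUD stratum 120 of 180, so two thirds of each arm (60 of 90).
- Alpha 0.05, taken here as two-sided; chi-square test.

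**Assumptions**
- r: actual referral rate from usual care, equal in both arms, so the true difference is zero.
- d: share of the remaining Veterans for whom a clinician charts a declined offer, equal in both arms.
- k: share of TAU+RA AUD participants whose agent note records a declined offer and meets the definition, independent of usual-care scoring.

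**Formulas**
- Scored in TAU: u = r + (1 − r)d
- Agent-note share of the arm: s = (2/3)k
- Scored in TAU+RA: s + (1 − s)u

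**Numbers for r = 20%, d = 20%.** u = 0.20 + 0.80 × 0.20 = 36%.
- k = 10%: 0.0667 + 0.9333 × 0.36 = 40.3%
- k = 25%: 0.1667 + 0.8333 × 0.36 = 46.7%
- k = 50%: 0.3333 + 0.6667 × 0.36 = 57.3%

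The chance of a significant result favouring TAU+RA, by exact binomial enumeration:

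| k | Scored, TAU+RA v TAU | Chi-square, 90 per arm | Fisher, 90 per arm | Fisher, 63 per arm |
|---|---|---|---|---|
| 10% | 40.3% v 36% | 0.09 | 0.07 | 0.05 |
| 25% | 46.7% v 36% | 0.31 | 0.26 | 0.19 |
| 50% | 57.3% v 36% | 0.81 | 0.77 | 0.64 |

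With k = 0 and 90 per arm, the Fisher figure is 0.018.

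**Sensitivity to clinician charting (Fisher, r = 20%, 90 per arm).** With d = 0, k = 25% and 50% give 0.47 and 0.96. With d = 40%, they give 0.15 and 0.54. The more often clinicians chart declined offers, the smaller the distortion.

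**Sensitivity to stratum.** The plan expects Veterans with AUD to be referred more often in either arm, so agent notes would overlap more with usual-care scoring. TAU is held at 36% overall, and the agent's effect is confined to the AUD stratum.
- Usual-care scoring of 45% (AUD) and 18% (risky): TAU = (2/3)(0.45) + (1/3)(0.18) = 36%. The TAU+RA AUD rate is 0.45 + 0.55k. Overall this is 45.2% at k = 25% and 54.3% at k = 50%; chi-square 0.23 and 0.70.
- Usual-care scoring of 50% and 8%: the TAU+RA AUD rate is 0.50 + 0.50k. Overall this is 44.3% and 52.7%; chi-square 0.18 and 0.62.

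The stratum assumption therefore matters: at k = 50% the chance falls from 0.81 to 0.70 or 0.62.

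**If some offers are accepted.** Take r = 20%, d = 20%, k = 50%, now counting every qualifying agent note, with a quarter of those offers accepted and referred. Actual referral in TAU+RA is (2/3)(0.5)(0.25) + (1 − 0.0833)(0.20) = 26.7%, against 20%: 6.7 points, Fisher 0.14 at 90 per arm. Scored referral is still 57.3% against 36%: 21.3 points, Fisher 0.77.

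**After the fix.** If discussion-only cases score as no in both arms, equal actual referral gives an expected difference of zero.

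**The case against.** **The flag may be meant to exclude these cases.** The plan speaks of referral as completed and of the percentage referred, and it separates discussion from referral actually made. That language fits excluding flagged cases. A reader might infer that the flag is collected and never used; the documents do not show that. They show only that no scoring rule is stated. This stands, and it makes the finding a gap with a foreseeable direction, not a demonstrated bias.

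**The agent's referrals are the intervention.** This stands for consults placed after a session, which are part of the effect under test and should count. It does not cover declined offers.

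**TAU can score declined offers too.** This also stands. It would be wrong to infer that only TAU+RA can score without an actual referral. The agent's note is an additional route, and the calculation allows for clinician charting in both arms.

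**The sources are incomplete.** The method follows a cited chart-review study, the abstraction form is still to be developed, and the report templates in Appendix B are not available here. How often a refusal would read as a documented discussion is unknown. That limits the size, not the textual point.

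**Related issues add little.** A reader might extend the criticism to brief intervention, since no sentence says outright that an agent session counts. However, the plan describes the agent as delivering brief intervention of the kind the clinician would ideally give, so counting it is evidently intended. The counselling window opens at screening, which affects both arms alike, and counselling dates are abstracted. Accepting self-report as a source is a defensible choice, with a concordance check planned.

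**Conclusion.** The point holds as a should-fix matter for one secondary outcome. Confidence is high that the definition, as written, lets a declined agent offer score as a referral and that no scoring rule resolves the flag.

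Confidence in the size is only moderate. It depends on assumed referral and charting rates, on note wording that is not in the documents, and on how usual-care referral differs between strata. Under the central assumptions at 90 per arm, the distortion is small if 10% of TAU+RA AUD participants have a qualifying note (0.09). It is appreciable at 25% (0.18 to 0.31 across the stratum assumptions) and large at 50% (0.62 to 0.81). A reader should not infer that a false positive is likely, only that the plan does not rule it out.

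**What to change.** 1. Define the main referral endpoint as an actual referral made: a consult placed, an appointment scheduled, or a documented referral to a non-VA service. Include consults that the study team places after an agent session.
2. State that cases flagged as discussion without referral score as no, and report them by arm as a separate category. Offers made by the agent then remain visible.
3. Carry the same rule into Dependent Variables and the referral analysis.

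The change is to scoring only; what the agent or clinicians offer is untouched. The flag is already planned, so the cost is a revised definition and one extra line of reporting. The downsides are lower scored rates, mainly in TAU+RA, and possibly a second look at charts already abstracted.

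Optional additions: report CPRS-only rates beside either-source rates; report clinician-delivered brief intervention beside the any-source rate; and acknowledge that the agent's chart note may reveal the arm to abstractors described as blinded.
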